4.3 Safety Endpoints

Safety will be assessed through summaries of DLTs, incidence and severity of AEs, specific laboratory abnormalities graded according to NCI-CTCAE, ECG, vital signs, and APX005M exposure.

All AE data collected will be listed by study site, cohort, participant number, and cycle day.

4.3.1 Extent of exposure and compliance

- The MTD is maximum dose for which <33% of DLT-evaluable participants experience a DLT (only Phase 1b)
- The RP2D will be established taking into account the MTD of APX005M (if applicable), as well as the nature, severity and causal relationship for all AEs. Prior to establishing the RP2D all participants enrolled in the Phase 1b portion of the study must be followed until PD, study discontinuation due to toxicity or at least 2 cycles
- The duration of treatment of each patient will be computed as the time in weeks from the date of the first dose of any investigational product until the last dose administration (APX005M or nivolumab)+ (21 days, one cycle)/7.
- The relative dose intensity (RDI) and its components will be described for each of the drugs administered in the study
- Dose intensity (DI) is defined as the drug dose delivered per time unit and is expressed as mg/kg (for APX005M) or mg (for nivolumab) per week. In the case of APX005M, the weight registered for each cycle will be used to calculate the administered dose in mg/kg (in case a cycle's weight is missing it will be imputed via the LOCF –last observation carried forward– method)
- Target dose intensity (TDI)
- Relative dose intensity (RDI) is the ratio of DI and TDI, and can be expressed as a percentage:

$$\text{RDI (\%)} = (\text{DI}/\text{TDI}) * 100$$
- Number of cycles administered per patient will be described
- Dose delays and dose reductions per patient and the reasons for these dose modifications will be described by patient.

4.4 Other Derived Variables

In the case that more derived variables than the ones described in this document are required for the analysis, they will be defined and described in the statistical report. Once the variables are created, it will be checked that their values are correct and that they represent exactly what it is expected.

5. GENERAL STATISTICAL METHODS

5.1 Sample Size

The sample size for the Phase 1b dose-escalation cannot be precisely estimated but depends upon the observed toxicities. Cohorts of 3 to 6 participants will be treated at each DL during dose escalation portion of the study. It is anticipated that approximately 18 participants will be treated in this portion of the study depending on the actual rate of DLTs.

Sample size for Phase 2 is calculated using the Simon optimal 2-stage design:

- Cohort 1 (inNSCLC): Assuming a false positive rate (α) of 0.1 (one-sided), a false negative rate (β) of 0.1, a response probability of poor drug (P0) of 22% and a response probability of good drug (P1) of 40%, first stage sample size (n_1) is 24 and the maximum sample size (n) is 45 response evaluable participants.
 - In the first stage, if there are 5 or less responses in 24 participants, the enrollment in this cohort will be stopped. Otherwise, if 6 or more responses are observed, 21 additional participants will be accrued in Stage 2 for total of 45. Enrollment may continue into Stage 2 while the planned number of participants for Stage 1 are followed for efficacy.
 - By the end of Stage 2, if 13 or less responses are observed in 45 participants, then no further investigation is warranted. If 14 or more responses are observed, the null hypothesis will be rejected, and true RR is 40%.
 - The sample size of 45 participants, provides 97% power to statistically test the null hypothesis of historical 6-month PFS rate (PFSR) of 60% versus the alternative hypothesis of 6-month PFSR rate of 80%. This calculation assumes exponential PFS, 1-sided 5% type I error rate, enrollment of participants for 8 months with 6 months of follow-up prior to conducting the final analysis.
- Cohort 2 (PD1-MM): Assuming α of 0.1 (one-sided), β of 0.1, P0 5% and P1 of 20%, n_1 is 12 and n is 37 response evaluable participants.
 - In the first stage, if there are no responses in 12 participants, the enrollment in this cohort will be stopped. Otherwise, if 1 or more responses are observed, 25 additional participants will be accrued in Stage 2 for total of 37. Enrollment may continue into Stage 2 while the planned number of participants for Stage 1 are followed for efficacy.
 - By the end of Stage 2, if 3 or less responses are observed in 37 participants, then no further investigation is warranted. If 4 or more responses are observed, the null hypothesis will be rejected and true RR is 20%.
 - The sample size of 37 participants, provides 92% power to statistically test the null hypothesis of historical 6-month PFSR of 19% (estimated for ipilimumab following nivolumab or pembrolizumab) versus the alternative hypothesis of 6-month PFSR rate of 38%. This calculation assumes exponential PFS, 1-sided 5% type I error rate, enrollment of participants for 8 months with 6 months of follow-up prior to conducting the final analysis.
- Cohort 3 (PD1-NSCLC) Group A and Group B: Assuming α of 0.1 (one-sided), β of 0.1, P0 5% and P1 of 20%, n_1 is 12 and n is 37 response evaluable participants.
 - In the first stage, if there are no responses in 12 participants, the enrollment in that group will be stopped. Otherwise, if 1 or more responses are observed, 25 additional participants will be

accrued in Stage 2 for total of 37 per group. Enrollment may continue into Stage 2 while the planned number of participants for Stage 1 are followed for efficacy.

- By the end of Stage 2, if 3 or less responses are observed in 37 participants, then no further investigation is warranted. If 4 or more responses are observed, the null hypothesis will be rejected, and true RR is 20%.
- The sample size of 37 participants/group, provides 94% power to statistically test the null hypothesis of historical 6-month PFSR of 22% (estimated for chemotherapy regimens) versus the alternative hypothesis of 6-month PFSR rate of 43%. This calculation assumes exponential PFS, 1-sided 5% type I error rate, enrollment of participants for 8 months with 6 months of follow-up prior to conducting the final analysis.

5.2 Disposition of Study Participants

For participant study status, the number and percentage of participants for each one of the following categories will be presented by dose level and overall for Phase 1b and by cohort and overall for Phase 2 (including participants treated at RP2D in Phase 1b) in separate tables.

- Participants in Screened Population (the number only)
- Screen-failure participants (the number only)
- Enrolled participants (the number only)
- Participants in Safety Population
- Participants in Efficacy Population
- Participants in DLT Evaluable Population
- Participants who discontinued study treatment by primary reason
- Participants who discontinued study participation by primary reason

The data for participant disposition, protocol deviation, eligibility, and whether a participant is included in the analysis populations will be listed. Patients who discontinue treatment prematurely will be displayed in a listing, indicating the reason for such discontinuation.

5.3 Protocol Deviations

Deviations from the protocol, including violations of inclusion/exclusion criteria, will be assessed as “minor” or “major” by the clinical team. All protocol deviations will be collected separately from the database and listed.

All protocol deviations will be listed and major deviations from the protocol will lead to the exclusion of a patient from the EP.

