7.1 Sample Size Determination

This is a Phase 1b-2, study. The sample size for the Phase 1b dose-escalation cannot be precisely estimated but depends upon the observed toxicities. Cohorts of 3 to 6 subjects will be treated at each DL during dose escalation portion of the study. It is anticipated that approximately 18 subjects will be treated in this portion of the study depending on the actual rate of DLTs.

Sample size for Phase 2 is calculated using the Simon optimal 2-stage design [32]:

- **Cohort 1 (inNSCLC):** Assuming a false positive rate (α) of 0.1 (one-sided), a false negative rate (β) of 0.1, a response probability of poor drug (P0) of 22% and a response probability of good drug (P1) of 40%, first stage sample size (n1) is 24 and the maximum sample size (n) is 45 response evaluable subjects. In the first stage, if there are 5 or less responses in 24 subjects, the enrollment in this cohort will be stopped. Otherwise, if 6 or more responses are observed, 21 additional subjects will be accrued in Stage 2 for total of 45. Enrollment may continue into Stage 2 while the planned number of subjects for Stage 1 are followed for efficacy. By the end of Stage 2, if 13 or less responses are observed in 45 subjects, then no further investigation is warranted. If 14 or more responses are observed, the null hypothesis will be rejected and true RR is 40%.

The sample size of 45 subjects, provides 97% power to statistically test the null hypothesis of historical 6-month PFS rate (PFSR) of 60% (estimated for pembrolizumab in Keynote-024 [33]) versus the alternative hypothesis of 6-month PFSR rate of 80%. This calculation assumes exponential PFS, 1-sided 5% type I error rate, enrollment of subjects for 8 months with 6 months of follow-up prior to conducting the final analysis.

- Cohort 2 (PD1-MM): Assuming α of 0.1 (one-sided), β of 0.1, P0 5% and P1 of 20%, n1 is 12 and n is 37 response evaluable subjects. In the first stage, if there are no responses in 12 subjects, the enrollment in this cohort will be stopped. Otherwise, if 1 or more responses are observed, 25 additional subjects will be accrued in Stage 2 for total of 37. Enrollment may continue into Stage 2 while the planned number of subjects for Stage 1 are followed for efficacy. By the end of Stage 2, if 3 or less responses are observed in 37 subjects, then no further investigation is warranted. If 4 or more responses are observed, the null hypothesis will be rejected and true RR is 20%.

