7.2 Populations for Analyses

All subjects receiving both investigational products will be included in the safety population.

Subjects evaluable for DLT are defined as those who meet study eligibility criteria, receive the entire planned dose of APX005M and nivolumab and have follow-up for at least 21 days (i.e., subject does not come off study for reasons other than toxicity).

Subjects evaluable for efficacy (tumor response) are defined as those who meet study eligibility criteria and have at least one on treatment (post baseline) tumor assessment.

Subjects evaluable for PK are defined as those who have adequate APX005M serum concentration-versus-time data to allow proper estimation of PK parameters.

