2.3.5 Replacement of Patients

- For Phase 1b of the study, all participants that are not DLT-evaluable will be replaced for the purpose of establishing MTD.
- For Phase 2 of the study, participants will be evaluated for tumor response approximately every 8 weeks following the first dose of investigational product. Participants that are non-evaluable for tumor response will be replaced.

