3.4 Efficacy Population

Participants evaluable for efficacy (tumor response) are defined as those who meet study eligibility criteria and have at least one on treatment (post baseline) tumor assessment.

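### SAP 5.3 drops subjects with a major deviation from the Efficacy Population, contrary to Protocol 7.2 and SAP 3.4, which can bias the primary ORR and shift the Simon error rates

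*SAP*

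**What the plan says.** The two definitions of the efficacy set agree. Protocol 7.2 begins: "Subjects evaluable for efficacy (tumor response) are defined as those who meet study eligibility criteria", and adds a single further condition, one post-baseline scan on treatment. SAP 3.4 admits "those who meet study eligibility criteria and have at least one on treatment (post baseline) tumor assessment". Neither mentions protocol deviations.

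SAP 5.3 adds a third condition: "major deviations from the protocol will lead to the exclusion of a patient from the EP". It covers deviations of every kind, with eligibility violations named as one kind, and has the clinical team grade each as minor or major. It does not define major, set a date for the grading, or require that it be done without knowledge of response. EP is missing from the SAP's abbreviation list; Efficacy Population is the natural reading.

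The clause reaches the primary endpoint because SAP 5.4.2 performs the efficacy analysis on the Efficacy Population. SAP 2.3.1 states that the study is open label. On replacement, SAP 2.3.5 says: "Participants that are non-evaluable for tumor response will be replaced". It does not say whether a subject excluded under 5.3 counts as non-evaluable.

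The decision rules in Protocol 7.1 count responses among evaluable subjects. For Cohort 1, "first stage sample size (n1) is 24 and the maximum sample size (n) is 45 response evaluable subjects".

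**The concern.** An eligible subject who was scanned and then had a major deviation is in the primary set under SAP 3.4 and out of it under SAP 5.3. A programmer cannot satisfy both. For ineligible subjects 5.3 changes nothing, because Protocol 7.2 already leaves them out. The conflict is therefore confined to eligible, scanned subjects with other major deviations.

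Nothing in the SAP prevents a deviation from being graded after the subject's response is known. Selection would not need intent. Protocol 3.4.1.4 prohibits other anticancer drugs and most radiotherapy during treatment, and subjects who are doing badly may be likelier to receive them. That is an inference; the documents give no deviation rates.

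Two things are at stake: the ORR estimate, whose denominator could depend on outcome, and the error rates of the go/no-go rules, which were calculated for fixed numbers of evaluable subjects.

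**Working it through.** **Inputs (Protocol 7.1).** The design error rates are given as "Assuming a false positive rate (α) of 0.1 (one-sided), a false negative rate (β) of 0.1".
- Cohort 1: p0 = 0.22, p1 = 0.40, n1 = 24, n = 45. Stage 1 rule: "if there are 5 or less responses in 24 subjects, the enrollment in this cohort will be stopped", so r1 = 5. Success needs 14 or more responses, so r = 13.
- Cohorts 2, 3A and 3B: p0 = 0.05, p1 = 0.20, n1 = 12, n = 37, r1 = 0, r = 3 (success needs 4 or more).
- Assumed, because the documents give no figure: the number of eligible, scanned subjects with a major deviation (1 to 5 per cohort), or the share of non-responders excluded (5% to 20%).

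**Formula.** P(reject) = Σ over x > r1 of Bin(x; n1, p) × P[Bin(n − n1, p) ≥ r + 1 − x]. At p0 this is alpha; at p1 it is power.

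**Plan's own figures.** Cohort 1: alpha 0.0937, power 0.900. Cohorts 2, 3A and 3B: alpha 0.0935, power 0.902. A full search for the smallest expected sample size under p0 returns exactly the stated designs (5/24, 13/45 and 0/12, 3/37). They are correct, and the stated 0.1 is a ceiling.

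**Case 1: only non-responders excluded, and replaced.** Suppose a cohort passes Stage 1, misses the final cut-off, and k non-responders are dropped and replaced. The cohort then succeeds if n + k subjects yield at least r + 1 responses, so n + k replaces n in the formula, with n1 unchanged. If the k exclusions occur in Stage 1, n1 + k and n + k are used.

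| k | Cohort 1 alpha, Stage 2 / Stage 1 | 37-subject cohorts alpha, Stage 2 / Stage 1 |
|---|---|---|
| 1 | 0.107 / 0.110 | 0.099 / 0.103 |
| 2 | 0.121 / 0.128 | 0.106 / 0.113 |
| 3 | 0.135 / 0.147 | 0.112 / 0.122 |
| 5 | 0.165 / 0.189 | 0.124 / 0.143 |

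As a proportion: if a share d of non-responders is excluded and replaced, the null rate among those kept is p0 / [p0 + (1 − p0)(1 − d)]. At d = 0.10 this is 0.22 / (0.22 + 0.78 × 0.90) = 0.2386 and 0.05 / (0.05 + 0.95 × 0.90) = 0.0552. Alpha becomes 0.156 and 0.122. Over d = 0.05 to 0.20 it runs from 0.121 to 0.253 in Cohort 1 and from 0.107 to 0.162 in the others.

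**Case 2: only non-responders excluded, not replaced, cut-offs kept as counts.** The response count does not change, so alpha does not change. The estimate does: 13 responders give 13/45 = 28.9%, but 13/41 = 31.7% if four non-responders are removed. Likewise 3/37 = 8.1% becomes 3/33 = 9.1%.

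**Case 3: exclusion unrelated to response, replaced.** Alpha and power are unchanged.

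**Case 4: exclusion unrelated to response, not replaced, losses in Stage 2, cut-offs fixed.** Here n − k replaces n. With k = 4:
- Cohort 1 (n = 41): power 0.900 to 0.816, alpha 0.094 to 0.049.
- 37-subject cohorts (n = 33): power 0.902 to 0.876, alpha 0.093 to 0.071.

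**The case against.** A reader might infer that the clause simply loosens the Simon false-positive rate. The documents do not support that. Alpha rises only in Case 1, which needs both selection on non-response and replacement. Protocol 2.2 sends the reader to Section 7.2 for the meaning of non-evaluable, and under 7.2 an eligible subject with one on-treatment scan is evaluable. On that definition these subjects would not be replaced. Replacement after a missed final cut-off also looks unlikely in practice: SAP 5.4.8 puts last enrolment at Q2-2020 and the primary analysis after all final visits, while SAP 7 cites an output file dated 04FEB2021. These points stand. What remains is that the SAP never states the replacement status of a subject excluded under 5.3.

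Higher figures can be produced. If 10% of all subjects were excluded, none of them a responder, and all were replaced, the null rates would be 0.22/0.90 = 24.4% and 0.05/0.90 = 5.6%, with alpha 0.179 and 0.124. That assumes complete selection on outcome as well as replacement, and nothing in the documents supports either.

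It can also be said that SAP 2.2.6 plans ORR and DoR in the safety population, and that SAP 5.2 lists deviations and population membership, so selective exclusion would be visible. This is real mitigation. But the safety-population result does not govern the Simon decisions, which use response-evaluable subjects. That set can also contain ineligible and never-scanned subjects, so it does not isolate the effect of 5.3.

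**Conclusion.** The contradiction is certain on the text, taking EP as Efficacy Population: SAP 5.3 changes the primary ORR set in a way that Protocol 7.2 and SAP 3.4 do not allow, through an open-label judgement with no stated criteria or timing. It concerns only eligible, scanned subjects with other major deviations.

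The size and direction of the effect are not fixed by the documents. Alpha can pass 0.10 if excluded non-responders are replaced; a single exclusion is enough in Cohort 1. Without replacement, the cost is an inflated ORR if exclusion is selective, or lost power together with a lower alpha if it is not. All the scenario figures rest on assumed numbers of exclusions. The finding is that the plan leaves a primary-endpoint rule open to these outcomes, and does not show that any of them occurred.

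**What to change.** Delete the exclusion clause from SAP 5.3. Use the Protocol 7.2 / SAP 3.4 set for the primary ORR and for both Simon counts, so that eligible, scanned subjects with other major deviations stay in. If an analysis without major deviators is wanted, give it as a sensitivity analysis, with the criteria for major written down and applied without reference to response.

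The cost is one SAP sentence and one optional table. The reported ORR may be slightly lower than under the present clause.

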5.4 Summary of Statistical Methods

Participants treated at the RP2D in Phase 1b will be included in Stage 1 of the relevant disease-specific cohort for Phase 2. All the data (e.g., safety and efficacy) from these participants will be used in the relevant summary tables and listings for both Phase 1b and Phase 2 (including participants treated at RP2D in Phase 1b).

All relevant participant data will be included in listings. All participants entered into the database will be included in participant data listings. The listings will be generally sorted by first dose level (Phase 1b) or

cohort (Phase 2, including participants treated at RP2D in Phase 1b) and then Participant ID, unless specified otherwise.

All applicable data will be summarized by dose level and overall for Phase 1b, and by cohort and overall for Phase 2 (including participants treated at RP2D in Phase 1b), unless specified otherwise. In addition, data will be summarized by visit and/or time-point when appropriate. Unscheduled or repeat assessments will not be included in summary tables but will be included in listings.

Continuous variables will be summarized using the number of observations (n), mean, standard deviation (SD), median, Q1, Q3, minimum, and maximum along with the total number of patients contributing values.

Descriptive statistics for categorical/qualitative data will include frequency counts and percentages. The total number of participants in the dose level or cohort (N) will be used as the denominator for percent calculations, unless stated otherwise in the table footnote.

Kaplan-Meier model will be used to analyze duration of response, PFS and OS. In all these analyses, in addition to the Kaplan-Meier curve, median, Q1, Q3 and their corresponding CI 95%, number of events and censored cases distribution will be shown.

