1.2.4 Summary of the Known and Potential Risks and Benefits

Symptoms associated with cytokine release syndrome (including but not limited to flushing, itchiness, chills, fever, rash, tachycardia, hypotension, hypertension, rigor, and myalgia) after administration of APX005M are possible and have been observed in some of the subjects receiving APX005M. Guidance for monitoring and management of cytokine release syndrome are included in this protocol and in the APX005M Investigator's Brochure.

Transient transaminase elevations (\leq Grade 2) have been observed in several subjects with liver metastases, which were not associated with a particular dose of APX005M. Six subjects with liver metastases enrolled in the study experienced a transient increase in total bilirubin. Liver function test abnormalities tend to resolve to baseline within 7 days from APX005M administration.

Transient decreases in peripheral blood lymphocyte count in general and B-cell count in particular have been observed for APX005M as well as for other CD40-agonistic mAbs, and are believed to be a PDn effect. Transient decreases in platelet counts were observed for some of the subjects receiving higher doses of APX005M but were not associated with bleeding or other clinical manifestations.

Other symptoms might also occur, including allergic reactions, which could be severe, pulmonary edema, and rarely, thromboembolic events, myocardial infarction and/or death.

In the recently completed Phase 1 study APX005M-001, APX005M demonstrated a dose-dependent activation of APCs, T cell activation and increases in circulating levels of cytokines.

The biological effects and the overall tolerability of APX005M up to 1mg/kg body weight suggest a best in class profile for APX005M and the possibility of a safe and tolerable combination with other immunomodulatory antibodies such as nivolumab.

Please refer to the most recent version of the APX005M Investigator Brochure for the most current summary of APX005M to date.

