- **Grade 2-3:** treat with IV or oral corticosteroids until symptoms improve to Grade 1 or less. Consider renal biopsy with nephrology consult.
- **Grade 4:** treat with IV corticosteroids followed by oral corticosteroids until symptoms improve to Grade 1 or less. Add prophylactic antibiotics for opportunistic infections. Consider renal biopsy and consult nephrologist.

- **Pneumonitis**

- **Grade 2:** request pulmonary and infectious disease consults. Treat with IV or oral corticosteroids until symptoms improve to Grade 1 or less. Consider bronchoscopy, lung biopsy and hospitalization.
- **Grade 3-4:** request pulmonary and infectious disease consults. Hospitalize and treat immediately with IV corticosteroids. Administer additional anti-inflammatory measures, as needed. Add prophylactic antibiotics for opportunistic infections. Consider bronchoscopy and lung biopsy.
- **Liver Function Tests**
 - **Grade 2:** monitor liver function tests more frequently until returned to Grade 1 or less. If no improvement in 5-7 days, treat with IV or oral corticosteroids until symptoms improve to Grade 1 or less.
 - **Grade 3 and 4:** treat with IV corticosteroids for 24-48 hours followed by oral corticosteroids until symptoms improve to Grade 1 or less. If no improvement in 3-5 days administer additional immunosuppressive measures (e.g. mycophenolate mofetil), as needed. Add prophylactic antibiotics for opportunistic infections. Consult gastroenterologist.
- **Endocrinopathy**
 - **Asymptomatic TSH abnormality:** monitor fT4 if TSH is $<0.5 \times \text{LLN}$, $> 2 \times \text{ULN}$ or consistently out of range in two subsequent measurements. Consider endocrinology consult.
 - **Symptomatic endocrinopathy:** evaluate endocrine function and consider a pituitary scan. For abnormal laboratory results/pituitary scan initiate IV corticosteroids followed by oral or IV corticosteroids until symptoms improve to Grade 1 or less. Initiate appropriate hormone therapy. For normal laboratory results/pituitary scan repeat labs in 1-3 weeks and pituitary scan in 1 month.
 - **Suspicion of adrenal crisis:** rule out sepsis, administer IV fluids. Consult endocrinologist and if adrenal crisis is ruled out, treat as for symptomatic endocrinopathy. Otherwise, administer stress dose of IV steroids with mineralocorticoid activity.
- **Skin Adverse Events**

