7.3.2 Secondary Endpoints

- Incidence and severity of AEs and specific laboratory abnormalities graded according to NCI-CTCAE, v4.03
- 6-month PFSR by cohort/group (Phase 2), defined as the proportion of subjects that did not have disease progression (by RECIST 1.1) or died due to any cause at 6 months from the first dose of investigational product
- DOR (by RECIST 1.1) by cohort/group, defined as the time from the first evidence of confirmed PR or better to disease progression or death due to any cause
- PFS (by RECIST 1.1) by cohort/group, defined as time from first dose of investigational product to the earlier of PD or death due to any cause.

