2.2.2 Secondary Objectives

- Evaluate safety of the APX005M and nivolumab combination by analysing the incidence and severity of AEs and specific laboratory abnormalities graded according to NCI-CTCAE, v4.03
- Evaluate the 6-month progression-free survival (PFS) rate (PFSR) in each cohort/group (Phase 2 only)
- Evaluate duration of response (DoR) in each cohort/group by RECIST v1.1 (Phase 2 only)
- Evaluate the median PFS by cohort/group by RECIST v1.1 (Phase 2 only)

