5.4.3.4 Clinical Laboratory Evaluation

The following laboratory tests will be performed locally to evaluate the safety profile: serum chemistry (including thyroid tests), hematology (including coagulation), urinalysis, and pregnancy. Except for urinalysis and pregnancy tests which are scheduled at Screening only, the other tests will be performed at Screening, Treatment Phase and End of Treatment (EOT).

For each laboratory parameter, the actual will be summarized and the frequency of participants with clinically significant abnormal laboratory values will be tabulated for baseline and each scheduled post baseline visit, by dose level and overall for Phase 1b and by cohort and overall for Phase 2.

All serum chemistry, hematology and urinalysis data will be listed by participant; the clinically significant abnormal values will be flagged. The pregnancy results will also be listed.

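### The SAP specifies no CTCAE-graded laboratory table and leaves unscheduled values out of its summaries, so the laboratory part of a secondary endpoint has no specified analysis

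*SAP*

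**What the plan says.** **The endpoint.** Protocol 7.3.2 lists as a secondary endpoint: "Incidence and severity of AEs and specific laboratory abnormalities graded according to NCI-CTCAE, v4.03". SAP 2.2.2 repeats it as the means of meeting the safety objective ("incidence and severity of AEs and specific laboratory abnormalities graded according to NCI-CTCAE, v4.03"). SAP 4.3 says that safety will be assessed through summaries that include "specific laboratory abnormalities graded according to NCI-CTCAE".

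**The laboratory analysis.** SAP 5.4.3.4 is the only section that specifies laboratory tables. For each parameter the actual values are summarised, and "the frequency of participants with clinically significant abnormal laboratory values will be tabulated for baseline and each scheduled post baseline visit". For listings, "All serum chemistry, hematology and urinalysis data will be listed by participant; the clinically significant abnormal values will be flagged". The section names no CTCAE grade, no worst post-baseline value and no shift from baseline, and it does not say which abnormalities are the specific ones in the endpoint.

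**The exclusion.** SAP 5.4, which governs all tables, states: "Unscheduled or repeat assessments will not be included in summary tables but will be included in listings". It makes no exception for safety laboratory data.

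**The adverse event route.** Under Protocol 6.3.6 a laboratory abnormality also goes on the adverse event page if it leads to a product being stopped, delayed or interrupted, needs corrective therapy, is clinically significant, or is serious. Protocol 6.2.2 has the highest grade recorded. SAP 5.4.3.3 tabulates events of Grade 3 or higher and events by maximum grade.

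**The concern.** Two gaps compound each other. First, the endpoint asks how many participants had an abnormality and how severe it was by grade. The specified table answers how many were flagged at each visit on a judgement of clinical significance, which is not a severity scale. Second, the values most likely to be extreme in a participant with toxicity may come from extra draws, and these are barred from the tables.

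At stake are the laboratory component of a stated secondary endpoint and the direction of error in a safety result: the laboratory tables would tend to make the combination look milder than the collected data show.

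**Working it through.** The documents give no figure on this point to reproduce, so the check is mainly a comparison of texts.

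**1. Promise against specification**

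| Element of the endpoint | Promised in | Specified in SAP 5.4.3.4 |
|---|---|---|
| CTCAE grade | Protocol 7.3.2; SAP 2.2.2, 4.3 | No; a clinical-significance flag only |
| Incidence per participant | Protocol 7.3.2; SAP 2.2.2 | No; counts per scheduled visit |
| Named abnormalities | Implied by the word specific in all three | No list |
| Change from baseline | Protocol 7.4.2 | No; actual values only |

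**2. Visit counts are not incidence.** One participant flagged at three visits and three participants flagged at one visit each both add 3 to the column of visit counts. The incidences are 1 and 3 participants. Without an any-time post-baseline count, the table cannot tell them apart.

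**3. Direction of the exclusion.** For one participant let S be the grades at scheduled draws and U those at unscheduled or repeat draws. Then max(S) ≤ max(S and U together), with equality only when the worst grade also occurs at a scheduled draw. Summed over participants, the number reaching any given grade from S alone cannot exceed the number from all values. The error runs one way.

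**4. Some extra draws are caused by toxicity.** For Grade 2 liver tests, Protocol 3.4.1.2 says: "monitor liver function tests more frequently until returned to Grade 1 or less". Protocol 3.6 calls for weekly re-evaluation when retreatment criteria, which include blood counts, are not met. Such draws lie outside the visit schedule in Protocol 5.1, so the excluded values are not a random subset.

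**5. How much the schedule leaves to extra draws (illustration only).** Phase 2 schedules chemistry and haematology on Days 1 and 8 of a 21-day cycle, giving gaps of 7 and 14 days. Phase 1b Cycles 1 and 2 use Days 1, 2, 3, 8 and 15, giving gaps of 1, 1, 5, 7 and 7 days. Assume that onset is uniform over the cycle. The share of episodes of length L days lying wholly between scheduled draws is the sum of max(0, gap − L) divided by 21.

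| L (days) | Phase 2 | Phase 1b, Cycles 1–2 |
|---|---|---|
| 3 | (4+11)/21 = 71% | (2+4+4)/21 = 48% |
| 5 | (2+9)/21 = 52% | (0+2+2)/21 = 19% |
| 7 | (0+7)/21 = 33% | 0% |
| 14 | 0% | 0% |

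These are shares that only an extra draw could reveal. They are not an estimate of what the SAP loses, because many such episodes would never be sampled. Clustering of onset just after dosing would change the shares. Short episodes are plausible here: Protocol 1.2.4 says "Liver function test abnormalities tend to resolve to baseline within 7 days from APX005M administration".

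**6. What the adverse event route leaves uncovered.** Protocol Table 4 answers Grade 3–4 neutropenia and thrombocytopenia with holds, and Grade 3–4 transaminase rises with holds or discontinuation. When drug-related, these should generally meet Protocol 6.3.6. A cytopenia that recovers untreated before the next dose need not. Protocol 1.2.4 describes lymphocyte falls as a pharmacodynamic effect and platelet falls as transient and without bleeding. Table 4 has no lymphopenia row and Protocol 3.6 sets no lymphocyte threshold, so such a fall might be listed and never counted.

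**The case against.** The strongest reply is that the adverse event tables already do most of the work. Two of the four criteria in Protocol 6.3.6, a change to dosing and a need for corrective therapy, need no judgement of clinical significance. They capture many Grade 3–4 values whatever visit found them, and the grade recorded is the highest. Dose-limiting toxicities are identified from adverse event pages reviewed by the medical monitor (SAP 5.4.3.2), not from laboratory tables. This stands, and it rules out an inference that a reader might draw, namely that peak toxicities are lost from the report altogether.

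Other replies also have force:

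- A rise that nobody sampled is a matter of the visit schedule, and no table can recover it.
- A reader might suppose that most worst values lie in unscheduled draws. The documents do not show this, and the extra liver tests follow a Grade 2 value already detected.
- A reader might take the 7-day resolution of liver abnormalities as a sign of hidden Grade 3–4 peaks. The same paragraph of Protocol 1.2.4 describes the transaminase elevations seen as Grade 2 or lower.
- Leaving unscheduled values out of by-visit summaries is ordinary practice, and the sentence in SAP 5.4 follows one about summaries by visit. It is not limited to them, however.
- The table shells are in a separate file (SAP section 7) that could not be checked. They may contain graded tables.

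What remains is that SAP 4.3 promises graded laboratory summaries and SAP 5.4.3.4 does not specify them. The endpoint names laboratory abnormalities alongside adverse events, so adverse event tables alone do not answer it.

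**Conclusion.** The point holds for the laboratory component of the secondary endpoint. In the SAP text that component has no graded per-participant summary, and the general exclusion keeps worst values from unscheduled or repeat draws out of the laboratory tables. Laboratory severity shown there can be understated and cannot be overstated by this rule.

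The size cannot be derived. It depends on how many worst grades came from extra draws and how many of those were not reported as adverse events; the documents give neither, and any percentage under-count would be a guess. The loss lies mainly in abnormalities that do not become adverse events, such as transient asymptomatic cytopenias. The graded adverse event component is delivered, all values are listed, and neither the primary endpoint nor the identification of dose-limiting toxicities is affected. That the endpoint will go unreported is not shown, because the shells were not available. The change should be made, but the trial does not turn on it.

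**What to change.** 1. In SAP 5.4, limit the exclusion of unscheduled and repeat assessments to by-visit descriptive summaries.
2. In SAP 5.4.3.4, name the laboratory parameters that make up the endpoint.
3. For each of them, in the Safety Population, add a table of worst post-baseline CTCAE v4.03 grade per participant and a shift table from baseline grade to worst grade. Use all post-baseline values, including unscheduled and repeat ones.
4. Keep by-visit summaries of actual values on scheduled visits only.
5. Align the external table shells if they differ.

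The cost is a few tables from data already collected and listed. Where a grade depends on the local reference range, that range must be in the database; the LDH subgroup in SAP 2.2.5 implies that at least some are. Reported laboratory abnormality rates may rise. SAP section 7 notes that the Phase 1b report was produced under version 1.0, so for Phase 1b the tables would be a supplement.
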